### **5.2.3.1 Criteria for Discontinuation from Treatment**

Study treatment may be discontinued for any of the following reasons:

- Any clinical AE, laboratory abnormality, or intercurrent illness that would, in the judgment of the Investigator, affect assessments of clinical status to a significant degree
- Toxicity that, despite maximum medical management, in the judgment of the Investigator, compromises the ability to continue study-specific procedures or is considered to not be in the patient's best interest
- Disease progression (based on Investigator assessment of baseline and post-baseline scans as per RECIST 1.1). In some circumstances patients may be treated beyond disease progression. Details are provided in Section [5.2.5](#).
- Patient request to discontinue treatment for any reason
- Patient noncompliance
- Initiation of systemic antineoplastic therapy other than treatments per protocol in the absence of progression
- Discontinuation of the study treatment at the request of Nektar, a regulatory agency or an institutional review board (IRB) or independent ethics committee (IEC)
- Pregnancy during treatment
- Death
- Investigator's decision, in consultation with the Medical Monitor

If a patient discontinues NKTR-255, the patient may continue on cetuximab alone, at the discretion of the Investigator, until disease progression or initiation of systemic anti-tumor therapy (whichever is earlier).

If a patient discontinues study drug(s), every attempt should be made to continue tumor assessment at every 9 weeks until disease progression or initiation of systemic anti-tumor therapy. The patient will be asked to attend the 60-day post-treatment follow-up assessment visit when discontinuing from the study treatment.

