## 7.4 Causality Relationship of AEs

The relationship of each AE to each study drug (NKTR-255 and cetuximab) as applicable will be evaluated by the Investigator using the following definitions:

- Not related: The AE is considered not related to the study drug(s). The AE can be reasonably explained by other factors such as the patient's pre-existing medical condition, underlying disease, concurrent illness, or concomitant medications/therapies.
- Related: The AE is considered related to the study drug(s). A plausible temporal sequence exists between the time of administration of the study drug and the development of the AE, or it follows a known response pattern to the investigational product. The AE cannot be reasonably explained by the known characteristics of the patient's clinical state or other concomitant therapies or interventions administered to the patient.

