## 9.6 Planned Analyses

### 9.6.1 Safety

Safety assessments will include Safety Population with treatment-emergent AEs with categorization of treatment related with incidences of serious and severe ( $\geq$  Grade 3) AEs, clinical laboratory tests including cardiac function tests, vital signs, physical examinations, and ECGs.

Adverse events and toxicity severity will be evaluated according to NCI-CTCAE Version 5.0 toxicity grading system. Safety assessments will be performed by medical review of AEs, vital signs, and laboratory results.

The incidence rate of DLTs will be evaluated by dose level for the DLT Population. Treatment-emergent AEs will be summarized by preferred term, system organ class, NCI-CTCAE grade of severity, and relationship to the study treatment by dose level for Phase 1b (Dose Escalation), CCI [REDACTED] for the Safety Population. All TEAEs will be summarized by incidence, severity, and relationship to study drug(s).

A TEAE is defined as (regardless of intensity), any AE that occurs after initiation of study treatment on C1D1 until 60 days (inclusive) after the last dose of study treatment. Adverse events with a starting date after the start of new anti-cancer therapy are not considered TEAEs.

Vital signs (including change in weight) and clinical laboratory test results will be summarized descriptively by dose level in Phase 1b (Dose Escalation) CCI [REDACTED] [REDACTED] for the Safety Population. A listing and summary of patients who discontinued study drug(s) due to an AE will be provided.

A data listing for deaths will be provided.

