**Treatment-emergent adverse events (TEAE):**

- Any AE that occurs after study treatment initiation.
- An AE that was present at the time of study treatment initiation but worsened after study treatment initiation.
- An AE that was present and resolved prior to treatment and reappeared after treatment initiation.
- Any treatment-related AE will always be considered treatment-emergent.

**NKTR-255 Treatment-emergent adverse events (TEAE) period:** Start of NKTR-255 through 30 days post last dose NKTR-255, or until a new antineoplastic regimen has been initiated, whichever comes first.

**Extended treatment-emergent adverse events (TEAE) period:** Start of any study drug through 60 days post last dose of study drug, or until a new antineoplastic regimen has been initiated, whichever comes first.

**Prior medications:** Prior medications are defined as medications with start date prior to C1D1.

**Concomitant medications:** Concomitant medications are defined as medications with stop date after C1D1, or medications with start date on or after C1D1 and up to 30 days after the last dose of NKTR-255. Medications with a start date after the initiation of any subsequent anticancer treatment will not be considered concomitant medications.

Medications with start date prior to C1D1 and end date after C1D1 will be classified as both prior and concomitant medications.

**Best overall response (BOR):** The BOR is defined as the confirmed best response designation over post-baseline response assessments. Disease assessments beyond progression or after start of subsequent therapy will not be considered for BOR.

**Overall response rate (ORR):** The ORR is defined as the proportion of subjects who have achieved PR or better as their BOR.

**Complete response rate (CRR):** The CRR is defined as the proportion of subjects who have achieved CR as their BOR.

**Responders:** Responders are defined as subjects with a confirmed BOR of PR or better. Ongoing responders are defined as responders who have not progressed, not died, not been off study and not started a subsequent therapy.

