For IRR (except for the PT of infusion related reaction), events that start within 48 hours after NKTR-255 drug administration will be included. If AE onset time is available, the time information will be used to exclude events that start before dosing and include events that start on day 3 relative to dosing day but within 48 hours of start of NKTR-255 administration; otherwise, AEs that start on the same and next day of dosing will be included. Analysis on IRR will only be performed for patients who receive at least one NKTR-255 dose.

The following summaries will be performed for OSO using safety population with TEAE period. A listing of how OSO is categorized will also be provided.

- Treatment-emergent Other Safety Observations (OSO) by Category/PT and Worst CTC Grade
- Grade 3 and above Treatment-emergent Other Safety Observations (OSO) by Category/PT
- Treatment-emergent Other Safety Observations (OSO) Related to NKTR-255 by Category/PT and Worst CTC Grade
- Serious Treatment-emergent Other Safety Observations (OSO) by Category/PT and Worst CTC Grade
- Serious Treatment-emergent Other Safety Observations (OSO) Related to NKTR-255 by Category/PT and Worst CTC Grade

Additionally, site identified Treatment-emergent CRS events will also be summarized and listed by PT and Worst CTC Grade.

The following AE summaries will be provided in enrolled population with extended TEAE period:

- Overall summary of Extended TEAEs
- Extended TEAE Related to any Study Drug by SOC, PT and Worst CTC Grade
- Serious Extended TEAE Related to any Study Drug by SOC, PT and Worst CTC Grade
- Grade 3 and above Extended TEAEs related to any Study Drug by SOC and PT
- Extended TEAE Leading to Discontinuation of any Study Drug by SOC and PT
- Extended TEAE Leading to death by SOC and PT

The following data listings will be provided in enrolled population:

- All TEAEs
- Serious TEAEs
- Grade 3 or Higher TEAEs
- Other Safety Observations (OSO)
- TEAEs Leading to Study Drug Discontinuation
- TEAEs Leading to Dose delay, Reduction, and Interruption
- TEAE leading to death

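### SAP 7.6.2 plans no general all-cause AE table by term beyond 30 days after the last NKTR-255 dose, although protocol 9.6.1 tabulates to 60 days after the last study treatment

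*SAP*

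**What the plan says.** Protocol 9.6.1 defines a treatment-emergent event as "any AE that occurs after initiation of study treatment on C1D1 until 60 days (inclusive) after the last dose of study treatment", leaving out events that start after new anti-cancer therapy. It summarises these events in the Safety Population by preferred term, system organ class, grade and relationship. Relationship is one way of breaking the events down there, not a condition for being counted.

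SAP 6.6.1 replaces this single window with two. The NKTR-255 period is "Start of NKTR-255 through 30 days post last dose NKTR-255, or until a new antineoplastic regimen has been initiated". The extended period is "Start of any study drug through 60 days post last dose of study drug", again cut short by a new antineoplastic regimen. SAP 7.6.2 ties the first period to the safety population and the second to the enrolled population.

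The safety-population list in SAP 7.6.2 has tables regardless of cause for any grade, serious, and Grade 3 and above events. In the enrolled-population list the counterparts are restricted. The table covering any grade is titled "Extended TEAE Related to any Study Drug by SOC, PT and Worst CTC Grade". The one covering serious events is likewise limited, as its title shows: "Serious Extended TEAE Related to any Study Drug by SOC, PT and Worst CTC Grade". The table for Grade 3 and above has the same restriction. That list also has an overall summary and two tables by term without a relatedness filter, for events leading to discontinuation of any study drug and events leading to death. Listings of all, serious, and Grade 3 or higher events are planned in the enrolled population.

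SAP 12.0 records in one line that the TEAE period definition was updated.

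**The concern.** SAP 4.1 makes the incidence of treatment-emergent events part of the primary endpoint, with no relatedness condition. The trial is open-label and Phase 1b has no control arm, so whether an event counts as related rests on the investigator's judgement. Under protocol 7.4 a related event needs a plausible time sequence or a known response pattern, and it must also meet the condition "The AE cannot be reasonably explained by the known characteristics" of the patient's clinical state. Incidence by term regardless of cause is the usual protection against misattribution. In the later part of the observation window the SAP removes it.

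Two features of this trial make the later part relevant. Protocol 5.2.3.1 provides that "If a patient discontinues NKTR-255, the patient may continue on cetuximab alone", so some patients may still be on study treatment well after the NKTR-255 period has closed. Protocol 5.12 also warns of tumour-site necrosis, pain, ulceration or bleeding both during and after combination therapy. Those are events an investigator could reasonably ascribe to the cancer.

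**Working it through.** The plan states no figure to reproduce. The check is a count of tables and a comparison of windows.

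**Step 1: tables in SAP 7.6.2 by relatedness filter**

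| Table by term | Safety population, NKTR-255 period | Enrolled population, extended period |
|---|---|---|
| Any event, worst grade | all-cause, and NKTR-255-related | related to any study drug only |
| Serious, worst grade | all-cause, and NKTR-255-related | related to any study drug only |
| Grade 3 and above | all-cause, and NKTR-255-related | related to any study drug only |
| Leading to discontinuation | all-cause (NKTR-255) | all-cause (any study drug) |
| Leading to death | all-cause | all-cause |

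The extended period has 6 summaries: 1 overall count and 5 tables by term. Of those 5, 3 are related-only and 2 are unfiltered. The number of general all-cause tables by term (any grade, serious, Grade 3 and above) is 0.

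**Step 2: length of the gap against protocol 9.6.1**

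Count days from the last NKTR-255 dose, and let T be the days from that dose to the last dose of any study drug.

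- Protocol window ends on day T + 60.
- SAP general all-cause tables end on day 30.
- Gap = (T + 60) − 30 = T + 30 days.

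The values follow from the dosing schedule:

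- T = 0 (both drugs end on the same day, or NKTR-255 is last): 0 + 30 = 30 days.
- T = 14 (NKTR-255 on Day 1 and the last weekly cetuximab on Day 15 of the final cycle; 15 − 1 = 14): 14 + 30 = 44 days.
- Cetuximab continued alone: longer. Once T exceeds 30, the first T − 30 days of the gap are on treatment. As an assumed example, two more 21-day cycles of cetuximab alone give T = 14 + 42 = 56 and a gap of 86 days, of which 56 − 30 = 26 are on treatment.

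These are maxima for a patient, because new anti-cancer therapy closes both windows.

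**Step 3: what is lost inside the gap**

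Events judged related to any study drug remain in the extended tables. What drops out is the event judged unrelated that led neither to discontinuation nor to death, even if it was serious or Grade 3 or 4.

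**Step 4: whether another output covers it**

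- The other safety observations in SAP 7.6.2 use the safety population and the shorter period.
- Delayed DLTs (SAP 7.6.1) are tabulated by term, but protocol 5.5.1 frames DLTs as related events.
- SAP 7.6.3 covers deaths only.
- The overall summary is not by term, and listings give no incidence.

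**Step 5: whether the data exist**

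Protocol 7.2, 7.5 and 7.7 collect AEs and SAEs to 60 days after the last study treatment. The events are in the database; they are just not tabulated.

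**The case against.** The best defence is that the window change is declared in SAP 12.0, that protocol 9.1 leaves detailed definitions to the SAP, and that with approximately 30 planned patients a reader can go through the listings of serious and Grade 3 or higher events line by line. Nothing is concealed: the events are reported, but not aggregated. This lowers the stakes. It does not remove the point, because the SAP 12.0 entry speaks of a period definition, not of dropping all-cause tabulation after day 30, and it gives no reason. Nor does a listing supply incidence by term for a primary endpoint.

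Four stronger readings are tempting, and the documents do not support them.

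- A reader might infer that every extended table by term is restricted to related events. The discontinuation and death tables are not.
- A reader might infer that the run-in and patients who received only cetuximab are also a departure from the protocol. They are not: the protocol 9.6.1 window opens at C1D1, and the Safety Population in protocol 9.5 requires NKTR-255. There the SAP adds related-event tables that protocol 9.6.1 did not plan.
- A reader might express the loss as a fixed share of follow-up. The 30 days run from the last NKTR-255 dose and the 60 days from the last study drug, so no single share applies.
- A reader might want a number of affected patients. The documents give no rate of late events or of unrelated attribution from which to derive one. Nor do they show that late toxicity is in fact misattributed; they only make it possible.

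**Conclusion.** The point stands for patients who received NKTR-255. From day 31 after the last NKTR-255 dose to day 60 after the last study treatment, SAP 7.6.2 has no general all-cause table by term, where protocol 9.6.1 would give one. The gap is up to T + 30 days per patient: at least 30 days where follow-up is complete, and including on-treatment time when cetuximab continues alone for more than 30 days. The number of events involved is unknown.

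This rests on reading the table titles in SAP 7.6.2 as complete, and on the enrolled-population listings following the extended period, as the population rule in that section suggests. If those listings used the shorter period, coverage would be weaker still. It is a reporting gap with a cheap remedy, not a flaw in data collection.

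**What to change.** In SAP 6.6.1, define a window that matches protocol 9.6.1: from study treatment on C1D1 to 60 days inclusive after the last study treatment, excluding events that start after new anti-cancer therapy. In SAP 7.6.2, add three tables for the Safety Population over that window, regardless of relationship:

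- all events by SOC, PT and worst grade;
- serious events by SOC, PT and worst grade;
- Grade 3 and above events by SOC and PT.

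Place them beside the existing related-only tables. If the sponsor prefers not to produce them, SAP 12.0 should say that all-cause tabulation by term beyond 30 days after NKTR-255 is dropped, and why.

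The same three tables in the enrolled population for the extended period would add the run-in and the cetuximab-only patients. They are an optional addition, not a protocol requirement, and alone would not reproduce the protocol 9.6.1 analysis because both population and start date differ.

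The cost is three reruns of existing table programs with a different period flag, a few more tables in the report, and SAP wording. No new data are needed.

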### **7.6.3 Death**

All cause deaths will be summarized by dose level in the enrolled population:

- All deaths, reasons for death
- Deaths within treatment-emergent period, and reasons for death
- Deaths within extended treatment-emergent period, and reasons for death

A by-patient listing of deaths will be provided for all enrolled patients.

### **7.6.4 Clinical Laboratory Evaluation**

Clinical laboratory tests will be conducted according to the Schedule of Assessments and performed by the designated central laboratories. Analyses of laboratory parameters include values collected until 30 days after the last dose of NKTR-255, but before the initiation of subsequent anticancer treatment.

Below are the selected laboratory parameters with the direction of interest to be summarized:

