- a. All procedures and examinations should be performed before the administration of study drug(s) on dosing days, except as indicated. The acceptable visit window is + 1 day for Day 1. If scheduled visits or assessments coincide with a weekend or holiday, schedule at the next feasible date. Please contact the Medical Monitor to discuss any concerns about study visits or assessments that may fall out of the protocol-specified window because of unforeseen delays or other patient-specific circumstances. All out-of-window visits and procedures will incur a protocol deviation.
- b. The EOT visit should occur within 7 days after study treatment is discontinued, or before a new antineoplastic regimen has been initiated.
- c. Safety follow-up visit to occur 60 days after the last dose of study treatment. Survival follow-up visits will occur every 3 months from EOT.
- d. Includes previous immunotherapy, chemotherapy, targeted therapy, radiation therapy, prescription medications, over-the-counter medications, and herbal and dietary supplements.
- e. Patients with HNSCC must also have HPV and EBV status at Screening or provide historical assessment results.
- f. Brain MRI is only required for patients with a history of brain metastases. A standard-of-care brain MRI occurring prior to the 28-day screening window may be acceptable based on consultation with the Medical Monitor.
- g. See Section 7.13. Screening and End of Treatment physical examinations will be a complete physical examination. Symptom-directed physical examinations should be performed at the discretion of the Investigator to identify changes from baseline or to evaluate changes based on the patient's clinical symptoms during other clinic visits. The patient's height is measured at the Screening visit.
- h. The dose does not need to be recalculated for weight changes that are < 10% from baseline (Day -7).
- i. Vital signs to be recorded include temperature, pulse, respiration, systolic and diastolic blood pressure, and oxygen saturation (PaO2). PaO2 monitoring is required only at Screening and on dosing days. Collect vital signs before PK sample collection when both vital signs and PK samples are scheduled for the same timepoint, except EOI timepoint. CCI [REDACTED]  
[REDACTED]
- j. An echocardiogram or MUGA or nuclear scan for cardiac function and measurement of LVEF is required prior to dosing and may have been obtained within 60 days prior to C1D1.

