#### 5.3.1.6 Criteria to Resume NKTR-255

Patients will be permitted to resume study drug(s) at the same dose level(s) following resolution of the AE to Grade  $\leq 1$  or to baseline within 2 weeks after the completion of the prior cycle, with the exception of patients who meet criteria for permanent discontinuation as specified in Section 5.7.

Patients may resume treatment when the drug-related AE(s) resolve(s) to Grade  $\leq 1$  or baseline, with the following exceptions:

- Patients may resume treatment in the presence of Grade 2 fatigue.
- Patients with baseline Grade 1 AST/ALT or total bilirubin who require dose delays for reasons other than a 2-grade shift in AST/ALT or total bilirubin may resume treatment in the presence of Grade 2 AST/ALT **or** total bilirubin.
- Patients with combined Grade 2 AST/ALT **and** total bilirubin values meeting discontinuation parameters (see Section 5.7) should have treatment permanently discontinued.

A dosing delay lasting more than 2 weeks should be discussed with the Medical Monitor and the patient may resume the study if approved based on clinical assessment.

Tumor assessments should continue as per protocol even if dosing is delayed, and patients must otherwise meet the criteria for continued treatment at the time re-initiation of study therapy is considered.

If the decision is to resume study drug(s) dosing, the patient should restart treatment on the next regularly scheduled study drug(s) dosing visit. Skipped doses are not to be replaced.

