## 6.6 Definitions

### Run-in period:

Eligible patients on combination therapy will receive cetuximab 400mg/m^2 IV as a loading dose during the study run-in period (Day -7). The run-in period therefore starts from the time the patient receives cetuximab and ends when the patient receives combination treatment of NKTR-255 +cetuximab.

**Study drug or study treatment:** Study drug or study treatment refers to NKTR-255 or cetuximab.

**Study day:** Study Day 1 (C1D1) is the first day that the combination treatment of NKTR-255 +cetuximab begins.

**Baseline:** Unless otherwise specified, the baseline value for each variable is the last non-missing value collected at the time (if collected) closest to, but prior to, the start of NKTR-255 administration. For triplicate ECG data, the record with three non-missing value will be considered as non-missing. If multiple measurements occur on the same day at the same time, or on the same day but the time is not available, the average of the measurements (for continuous data) will be considered the baseline value. When dosing times and/or observation times are not collected, it is assumed that protocol planned in-office assessments obtained on the day of the first dose of study drug are prior to administration of the first dose of study drug and therefore considered baseline values.

**Last known alive date:** The date of last known alive date will be derived for patients unknown to have died or known alive at the analysis cut-off by using following dates:

- Patient assessment dates (blood draws **CCI** [REDACTED], vital signs, performance status, ECG, tumor assessments, ECOG, or tumor biopsy dates)
- Start and end dates of anti-cancer therapies administered after study treatment discontinuation
- AE start or end date
- Concomitant medication start or end dates
- Last date of contact collected on the 'Survival follow-up' eCRF (do not use date of survival follow-up assessment unless status is 'alive')
- Study treatment start or end date
- Date of discontinuation for study participation on disposition eCRF pages (do not use if reason for discontinuation is lost to follow-up)

Only dates associated with actual examinations of the patient will be used in the derivation. Dates associated with a technical operation unrelated to patient status such as the date a blood sample was processed will not be used.

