A listing of patients who met Hy's Law criteria will be provided. Hy's Law criteria are defined as follows:

- ALT  $\geq 3 \times \text{ULN}$  or AST  $\geq 3 \times \text{ULN}$
- Total bilirubin TBL  $\geq 2 \times \text{ULN}$
- ALP  $\leq 2 \times \text{ULN}$  or missing

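### Laboratory analyses stop 30 days after the last NKTR-255 dose, so values from the 60-day safety visit and other late follow-up miss the grade table and, on a plain reading, the Hy's Law listing

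*SAP*

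**What the plan says.** SAP 7.6.4 sets one window for all laboratory work: "Analyses of laboratory parameters include values collected until 30 days after the last dose of NKTR-255", and only those from before any new anticancer therapy begins. The CTC grade-increase table follows in SAP 7.6.4.2, and so does the Hy's Law output: "A listing of patients who met Hy's Law criteria will be provided". Neither is given a different window.

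For the safety visit, Protocol Table 1 footnote c says: "Safety follow-up visit to occur 60 days after the last dose of study treatment". The table header allows 14 days either side. SAP 6.6 defines the term to cover both drugs: "Study drug or study treatment refers to NKTR-255 or cetuximab". Protocol 5.2.3.1 lets a patient who stops NKTR-255 continue on cetuximab alone, and Protocol 5.2.6 follows clinically significant adverse events to resolution, return to baseline or permanent sequelae.

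For adverse events, Protocol 9.6.1 counts an event as treatment-emergent "until 60 days (inclusive) after the last dose of study treatment". SAP 6.6.1 splits this into an NKTR-255 period of 30 days and an extended period: "Start of any study drug through 60 days post last dose of study drug". SAP 7.6.2 and 7.6.3 use both periods, for adverse events and deaths respectively. No extended period is stated for laboratory values.

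**The concern.** The laboratory clock runs from the last NKTR-255 dose and stops at day 30. The safety-visit clock runs from the last dose of either drug to about day 60. Samples drawn between the two would be collected but would enter no laboratory summary.

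The patients with most to contribute after day 30 include those who stopped NKTR-255 with unresolved toxicity and those kept on cetuximab alone. Hepatic and hematologic abnormalities matter in this trial: Protocol 5.5.1 counts related Hy's Law cases, Grade 3 or higher transaminase or bilirubin elevations, and most Grade 4 hematologic events as DLTs. Protocol 5.5.3 has late events of this kind reviewed when the MTD is determined. A late hepatic signal could thus be a delayed DLT and still be absent from the two laboratory outputs meant to show it.

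**Working it through.** No figure in the plan needs reproducing. The check is a day count plus a comparison of outputs.

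**Inputs**
- Laboratory cut: day 30 after the last NKTR-255 dose (SAP 7.6.4).
- Safety visit: 60 ± 14 days after the last dose of either drug (Protocol Table 1, footnote c; SAP 6.6).
- L: days from the last NKTR-255 dose to the last dose of any study drug. L = 0 if NKTR-255 is last. L = 14 if weekly cetuximab runs to Day 15 of the final 21-day cycle. L = 63 is an illustrative nine weeks of cetuximab alone.
- EOT visit: within 7 days of stopping study treatment (Table 1 footnote b; Protocol 5.2.3.2).
- Cycle length: 21 days, or 28 days on maintenance.
- Hold: 2 weeks. Protocol 5.3.1.6 adds: "A dosing delay lasting more than 2 weeks should be discussed with the Medical Monitor". Protocol 5.7 mentions delays of up to 6 weeks from the last dose.

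**Step 1: safety visit.** Day after last NKTR-255 dose = L + 60 ± 14.

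| L | Earliest | Nominal | Latest | Days past cut, at earliest |
|---|---|---|---|---|
| 0 | 46 | 60 | 74 | 46 − 30 = 16 |
| 14 | 60 | 74 | 88 | 60 − 30 = 30 |
| 63 | 109 | 123 | 137 | 109 − 30 = 79 |

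No on-schedule visit falls inside the cut.

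**Step 2: dose holds.** A 2-week hold ends on day 21 + 14 = 35 or 28 + 14 = 42, which is 5 or 12 days past the cut. Six weeks from the last dose is day 42, also 12 days past. If NKTR-255 resumes, the last-dose date moves forward and every hold-period value counts. If it never resumes, values to day 30 still count and only later ones are lost.

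**Step 3: EOT visit.** Day = cycle length + hold + 0 to 7, assuming the stop is decided at the next dose date or at the end of a 2-week hold.

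| | No hold | 2-week hold |
|---|---|---|
| 21-day cycle | 21 to 28 (inside) | 35 to 42 (outside) |
| 28-day maintenance | 28 to 35 (may be outside) | 42 to 49 (outside) |

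An earlier decision brings the visit forward.

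**Step 4: tests at the 60-day visit.** Table 1 is broken in the text available. The PT/PTT, urinalysis and thyroid/lipase/amylase/CK rows end in the same two right-hand cells as the physical examination row, consistent with EOT and the 60-day visit. Lipase and amylase are among the parameters the SAP summarises; PT/PTT is not. The chemistry row, which holds the Hy's Law tests, is shifted by one cell and cannot be read with certainty.

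**Step 5: other outputs that could show a late result**

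| Output | End of window | Conditions |
|---|---|---|
| Grade-increase table | Day 30 after NKTR-255 | None beyond the window |
| Delayed DLTs (SAP 7.6.1) | None stated | Related adverse event meeting DLT criteria, in the DLT population |
| Extended TEAE tables (SAP 7.6.2) | Day 60 after either drug | Recorded as an adverse event; apart from the overall summary, also judged related or leading to discontinuation or death |
| Deaths (SAP 7.6.3) | Includes the extended period | Death |

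Protocol 7.12 records a laboratory result as an adverse event only if it is deemed clinically significant.

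**Step 6: an extended cut.** Sixty days after the last dose of any study drug takes in visits on days 46 to 60 of that clock. Visits on days 61 to 74 are still in window and are caught only if the nominal 60-day visit is named.

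**The case against.** The strongest reply is that serious late laboratory toxicity is reported elsewhere. Delayed DLTs have no stated end date and are listed by patient. SAP 6.6.1 treats any treatment-related adverse event as treatment-emergent, and the extended outputs run to 60 days after either drug. This stands for many serious events. It does not stand for results never recorded as adverse events, and a late event judged unrelated may appear only in the overall count and the listings. Adverse-event terms also do not replace graded shifts or paired transaminase and bilirubin screening.

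A second reply is that a 30-day window tied to the investigational drug is a reasonable attribution choice in an uncontrolled Phase 1b trial in advanced cancer. It matches the SAP's NKTR-255 TEAE period, and the protocol sets no window for laboratory summaries. This stands: the 30-day table should remain, and no departure from the protocol is shown. SAP Section 12 shows no legible entry for the laboratory cut, but one item there is redacted, so non-disclosure cannot be asserted.

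A reader might infer that all laboratory values from patients on hold are lost, or that a late Hy's Law case would go unreported altogether. The documents support neither. Values during a hold count if dosing resumes, and a related late case in a DLT-population patient, recorded as an adverse event, has its own output. That the cut governs the Hy's Law listing is itself inferred from the listing's place in the section; the SAP does not say whether its analyses include listings.

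**Conclusion.** The point holds in limited form. Every laboratory value later than day 30 after the final NKTR-255 dose is outside the grade-increase table and, unless the SAP states otherwise, outside the Hy's Law listing. Any value from an on-schedule 60-day visit is excluded by at least 16 days. EOT values are excluded only in some delayed or 28-day maintenance cases.

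Late laboratory toxicity can be understated in these outputs; the documents do not show that it is. The number affected is unknown. Patients who start new anticancer therapy leave the window under either rule, and it is not certain that the Hy's Law tests are drawn at the 60-day visit. The cut would still apply to chemistry taken after day 30 for other reasons, such as follow-up of an unresolved event.

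The primary Phase 1b endpoints, DLTs and TEAEs, are not computed from these outputs. This is a safety-reporting gap that is cheap to close.

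**What to change.** In SAP 7.6.4:

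- Keep the 30-day grade-increase table, labelled as the NKTR-255 period.
- Add a second run from the first NKTR-255 dose to 60 days after the last dose of any study drug, before new anticancer therapy. State that it includes the nominal 60-day visit anywhere in its 14-day window. It must start at the first NKTR-255 dose because SAP 6.6 takes baseline as the last value before NKTR-255, so run-in values cannot be post-baseline.
- State that the Hy's Law listing covers all values from the first dose of any study drug to the end of that same extended period. A listing needs no baseline, so it can start earlier.
- Record the laboratory windows in Section 12 if they are not already there.

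The cost is a few sentences and a second run of existing programs on data already collected. The downside is that some late abnormalities will reflect disease progression, which is why the 30-day table stays beside the extended one.
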